6.2.1.2.2. Patient’s Global Assessment of Disease Activity (PGADA)

PGADA is performed by patients. It is based on a 0 – 100 VAS, with a score of 0 indicating “very well” and 100 indicating “very poor” to the question “Considering all the ways psoriatic arthritis affects you, how well are you doing today?”.

6.2.1.2.3. Physician’s Global Assessment of Disease Activity (PhGADA)

PhGADA is performed by physicians. It is based on a 0 – 100 VAS with 0 indicates “no disease activity” and 100 indicates “maximum disease activity”.

6.2.1.2.4. Health Assessment Questionnaire Disability Index (HAQ-DI)

The HAQ-DI score is defined as the average of the scores of eight functional categories (dressing and grooming, arising, eating, walking, hygiene, reach, grip, and other activities), administered by the subject. Responses in each functional category are collected as: without any difficulty; with some difficulty; with much difficulty; unable to do a task in that area and with or without aids or devices. The HAQ-DI score ranges from 0 (no disability) to 3 (completely disabled), when 6 or more categories are nonmissing. Detailed algorithm for calculating HAQ-DI score is described in [Appendix 1](#).

HAQ-DI also includes a separate pain assessment and subject will be requested to mark the severity of the pain in the past week on a 0-100 VAS, with 0 indicating “no pain” and 100 indicating “severe pain”.

6.2.2. Primary Analysis of the Primary Efficacy Endpoint

To test for superiority of filgotinib 200 mg or filgotinib 100 mg group versus placebo control group in proportion of subjects who achieve ACR20 at Week 12, a logistic regression analysis with treatment groups and stratification factors in the model will be used. The model will include all treatment groups. Missing data on the ACR20 response rate at Week 12 will be imputed using multiple imputation (MI) assuming missing at random (MAR):

- The MI procedure replaces each missing binary ACR20 value with a set of plausible values that represent the uncertainty about the right value to impute. Twenty imputed datasets will be generated with starting seed 12345. These multiple imputed data sets are then analyzed by using the same method for the primary analysis for complete data as specified above. The results from each set of imputed data sets will then be combined using Rubin’s rule {[Rubin 1987](#)}. The stratification factors and treatment groups will be included in the imputation model as covariates and all available data at post-baseline visits up to Week 16 visit will be included in the longitudinal model.

The p-value from the logistic regression model with MI for testing the superiority of filgotinib 200 mg or filgotinib 100 mg as compared to placebo will be provided. The 2-sided 95% confidence interval (CI) of the ACR20 response rate at Week 12 based on MI method will be provided for each treatment group. In addition, treatment difference in ACR20 response rate at Week 12 between each filgotinib dose group and placebo group along with its 95% CI calculated based on MI method will be provided.

6.3. Key Secondary Efficacy Endpoints

The key secondary efficacy endpoints are:

- The proportion of subjects who achieve ACR50 response at Week 12
- Change from Baseline in HAQ-DI at Week 12
- Change from Baseline in SF-36v2 physical component summary (PCS) at Week 16
- Change from Baseline in LEI at Week 16, in subjects with enthesitis at Baseline
- The proportion of subjects who achieve PASI75 response at Week 16, in subjects with psoriasis covering $\geq 3\%$ of the BSA at Baseline
- The proportion of subjects who achieve MDA response at Week 16
- Change from Baseline in FACIT-Fatigue at Week 16
- Change from Baseline in LDI at Week 16, in subjects with dactylitis at Baseline

6.3.1. Definition of Key Secondary Efficacy Endpoints

6.3.1.1. ACR50

ACR50 is similarly defined as ACR20 (see Section 6.2.1), except that the improvement threshold from Baseline is 50%.

6.3.1.2. 36-Item Short-form Health Survey (SF36v2)

The SF-36 Version 2 is a 36-item, self-reported, generic, comprehensive, and health-related quality of life questionnaire that yields an 8 health domains (physical functioning, role-physical, bodily pain, general health, vitality, social functioning, role-emotional, and mental health). Each domain is scored by summing the individual items and transforming the scores into a 0 to 100 scale with higher scores indicating better health status or functioning. In addition, 2 summary scores, the physical component summary (PCS) score and the mental component summary (MCS) score will be evaluated based on the 8 SF-36 domains.

6.3.1.3. Enthesitis Assessments: Leeds Enthesitis Index (LEI)

The enthesitis examination by LEI is based on 6 anatomical sites: medial femoral condyle (left and right), lateral epicondyle (left and right) and the achilles tendon insertion (left and right). Enthesitis at each site was scored on a dichotomous basis: 0 means Enthesitis Absent and 1 means Enthesitis Present.

LEI is derived as the sum of the enthesitis score over the 6 sites mentioned above.

If there are missing items, then available data are used to derive LEI.

The summaries and analysis of LEI will be conducted on the FAS subjects with enthesitis at Baseline.

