6.3.1.5. Minimal Disease Activity (MDA)

MDA is a measure to indicate disease remission, and is based on a composite score of 7 domains.

A subject will be classified as having achieved MDA when at least 5 out of 7 of the following criteria are met.

- TJC68 ≤ 1,
- SJC66 ≤ 1,

- $PASI \leq 1$ for subjects with a Baseline psoriasis covering at least 3% of the BSA (or for subjects with a Baseline psoriasis covering $BSA < 3\%$, this criterion is considered met),
- Patent’s Global Assessment of PsA pain intensity (PGAPI) score ≤ 15 (0 – 100 VAS),
- $PGADA \leq 20$ (0 – 100 VAS),
- $HAQ-DI \leq 0.5$,
- Leeds Enthesitis Index ≤ 1 for subjects with enthesitis at Baseline (or for subjects without enthesitis at Baseline, this criterion is considered met).

In the case that some of the MDA components are missing, the MDA assessment will be based on the nonmissing components. If nonmissing components are not sufficient to determine the MDA response, then the MDA response will be considered as missing.

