6.3.1.7. Dactylitis Assessments: Leeds Dactylitis Index (LDI)

LDI measures the ratio of the circumference of the affected digit to the circumference of the digit on the contralateral hand or foot using a Leeds Dactylometer.

LDI score is calculated as follows:

$$\text{LDI score of a dactylitic finger/toe} = \left\{ \left[\left(\frac{A}{B} \right) - 1 \right] \times 100 \right\} \times C$$

where

A = circumference of the dactylitic finger/toe (mm)

B = circumference of the contralateral digit (mm)

C = tenderness score (0 = no tenderness, 1 = tender)

If both ipsilateral and contralateral digits are thought to be dactylitic, then the reference range (given at the foot of the Dactylitis Score Sheet as in Protocol Appendix 25) will be used as the comparator (i.e., B in the above formula).

Binary tenderness score is used in LDI score calculation due to lack of reliability in the original Ritchie index. {Healy 2007}

Total LDI score equals to the sum of the non-negative individual LDI scores across all fingers and toes. Negative individual LDI scores will not be included in the total LDI score.

If there are missing fingers or toes, then the missing individual scores for those fingers or toes will not be included in the total LDI score. For subjects with dactylitis status absent for all the fingers and toes, their total LDI scores will be set as 0, and the tenderness score for each finger and toe will also be set as 0.

The summaries and analysis of LDI will be conducted on the FAS subjects with dactylitis at Baseline.

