6.4.1. Definition of Other Secondary Endpoints

6.4.1.1. Tender Dactylitis Count (TDC)

Tender score (0 = no tenderness, 1 = tender, 2 = tender and wince, 3 = tender and withdraw) is collected for Dactylitis Assessments on the Dactylitis Score Sheet that was used for calculation of LDI total score.

Tender dactylitis count (TDC) equals the number of tender fingers and toes (tender score >0). For subjects with dactylitis status absent for all the fingers and toes, the TDC will be set as 0. This score is used as a component of the PASDAS.

If there are missing fingers or toes, then the missing count for those fingers or toes will not be included in the TDC.

6.4.1.2. Psoriatic Arthritis Disease Activity Score (PASDAS), PASDAS Low Disease Activity (LDA) and PASDAS remission

$$\text{PASDAS} = \left[0.18 \times \sqrt{\text{PhGADA}} + 0.159 \times \sqrt{\text{PGADA}} - 0.253 \times \sqrt{\text{PCS}} + 0.101 \times \ln(\text{SJC66} + 1) + 0.048 \times \ln(\text{TJC68} + 1) + 0.23 \times \ln(\text{LEI} + 1) + 0.377 \times \ln(\text{TDC} + 1) + 0.102 \times \ln(\text{CRP} + 1) + 2 \right] \times 1.5$$

where

PhGADA = Physician's Global Assessment of Disease Activity (0 – 100 VAS);

PGADA = Patient's Global Assessment of Disease Activity (0 – 100 VAS);

PCS = Physical Component Score of the SF-36;

LEI = Leeds Enthesitis Index, derived from the enthesitis assessments;

TDC = Tender Dactylitis Count from the LDI;

CRP is in the unit of mg/L.

A lower score indicates better function.

If a subject did not have dactylitis at baseline and hence no dactylitis assessments are collected post-baseline, then it is assumed that TDC = 0 at baseline and all post-baseline visits for calculating PASDAS.

If a subject did not have enthesitis at baseline and hence no enthesitis assessments are collected post-baseline, then it is assumed that LEI = 0 at baseline and all post-baseline visits for calculating PASDAS.

If any of the components is missing, then PASDAS remains missing.

PASDAS LDA is defined as $PASDAS \leq 3.2$; PASDAS remission is defined as $PASDAS \leq 1.9$.

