6.4.1.6. Modified Nail Psoriasis Area and Severity Index (mNAPSI)

mNAPSI is used to assess each nail abnormality for each of subject's nail. Three features or groups of features (pitting, onycholysis together with oil-drop dyschromia, and crumbling) of each fingernail will be graded on a scale from 0 to 3. Four features (leukonychia, splinter hemorrhages, hyperkeratosis, and red spots in the lunula) will be graded as either present (1) or absent (0) for each fingernail. Each finger will have a score between 0 and 13. The total mNAPSI score is the sum of all abnormalities individual score across all fingers, and the total mNAPSI score ranges from 0 to 130.

In case of one or more missing digits, the available digits will be used to calculate mNAPSI.

The summaries and analyses of nail psoriasis will be conducted on the FAS subjects who had psoriatic nail involvement at Baseline.

6.4.1.7. 12-item Psoriatic Arthritis Impact of Disease (PsAID-12)

The PsAID is calculated based on 12 numerical rating scales (NRS) questions. Each NRS is assessed as number between 0 and 10.

PsAID final value

$$\begin{aligned} &= (\text{PsAID1 (pain) NRS} \times 3) + (\text{PsAID2 (fatigue) NRS} \times 2) + \\ &(\text{PsAID3 (skin) NRS} \times 2) + (\text{PsAID4 (work and / or leisure activities) NRS} \\ &\times 2) + (\text{PsAID5 (function) NRS} \times 2) + (\text{PsAID6 (discomfort) NRS} \times 2) + (\\ &\text{PsAID7 (sleep) NRS} \times 2) + (\text{PsAID8 (coping) NRS} \times 1) + (\text{PsAID9 (anxiety)} \\ &\text{NRS} \times 1) + (\text{PsAID10 (embarrassment) NRS} \times 1) + (\text{PsAID11 (social life)} \\ &\text{NRS} \times 1) + (\text{PsAID12 (depression) NRS} \times 1) \end{aligned}$$

The total is divided by 20. Thus the range of the final PsAID value is 0-10 where higher figures indicate worse status.

If one of the 12 NRS values composing the PsAID is missing, the imputation is as follows: calculate the mean value of the 11 other (nonmissing) NRS (range, 0 – 10), impute this value for the missing NRS. Then, calculate the PsAID as explained above. If 2 or more of the NRS are missing, the PSAID is considered missing value (no imputation).

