6.4.1.12. Spondyloarthritis Research Consortium of Canada (SPARCC) Enthesitis Index

The enthesitis examination is based on the 16 anatomical sites: the medial epicondyle (left and right), the lateral epicondyle (left and right), the supraspinatus insertion (left and right), the bilateral greater trochanter (left and right), the quadriceps tendon insertion into superior border of patella (left and right), the patellar ligament insertion into inferior pole of patella or tibial tuberosity (left and right), the achilles tendon insertion (left and right), and the plantar fascia insertion (left and right). Enthesitis at each site was scored on a dichotomous basis: 0 means Enthesitis Absent and 1 means Enthesitis Present.

SPARCC Enthesitis Index is derived as the sum of the enthesitis score over the 16 sites mentioned above.

If there are missing items, then available data are used to derive SPARCC Enthesitis Index.

The summaries and analyses of SPARCC Enthesitis Index will be conducted on the FAS subjects with enthesitis at Baseline.

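### LEI and SPARCC have no scaling and no minimum number of assessed sites, so an enthesis not assessed scores the same as an unaffected one

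*SAP*

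**What the plan says.** SAP 6.3.1.3 scores each of 6 entheseal sites 0 or 1 and defines LEI as their sum. Its rule for incomplete examinations is "If there are missing items, then available data are used to derive LEI". SAP 6.4.1.12 does the same for SPARCC over 16 sites: "If there are missing items, then available data are used to derive SPARCC Enthesitis Index". Neither section gives a scaling factor or a minimum number of assessed sites. Protocol Appendix 23 lists the sites and has no missing-site rule.

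The scores are used in three places:
- Change in LEI at Week 16, in subjects with baseline enthesitis, is a key secondary endpoint analysed by MMRM (SAP 6.3, 6.3.2). Change in SPARCC is another secondary endpoint, summarised descriptively (SAP 6.4.2).
- LEI enters PASDAS (SAP 6.4.1.2), where "If any of the components is missing, then PASDAS remains missing".
- LEI of 1 or less is one of the seven MDA criteria (SAP 6.3.1.5).

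Elsewhere the SAP does deal with incomplete scores. Joint counts are prorated if at least half the joints are evaluable and are otherwise missing (6.2.1.2.1). FACIT-Fatigue is prorated with 7 or more of 13 items (6.3.1.6). HAQ-DI needs 6 of 8 categories (Appendix 1). PASI is missing if any component is missing (6.3.1.4).

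**The concern.** A sum that omits a 0/1 item equals the sum with that item set to 0. A site that nobody examined therefore counts as healthy.

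A positive site missed only after baseline looks like improvement in that subject. Missed only at baseline, it looks like worsening. Missed at both visits, it largely cancels, although any true change there is lost.

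Nothing downstream catches this. The MMRM receives a number, not a gap. PASDAS is set to missing only when a component is missing, and a partly examined LEI is not missing. The general rule in SAP 6.1, which sets continuous composites to missing when a component is missing, applies unless specified otherwise. LEI and SPARCC have their own rules and are not in that section's list of composites. SAP 6.5 rules out sensitivity analyses. At stake are the LEI key secondary estimate, the SPARCC summaries and, through LEI, PASDAS.

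**Working it through.** The plan states no figure on this point, so there is none to reproduce. The steps below apply its own scoring formulas. The documents give no number of missing sites, so the values of m and q are assumptions.

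**1. Expected score.** Inputs: 6 sites scored 0/1 (SAP 6.3.1.3), k truly positive, m unassessed at random.
- As written: expected LEI = k × (6 − m)/6. For k = 3 and m = 1, 2, 3: 3 × 5/6 = 2.5; 3 × 4/6 = 2.0; 3 × 3/6 = 1.5.
- Prorated as for joint counts, (sum / sites assessed) × 6: expectation 3.0 in all three cases.
- SPARCC, 8 of 16 positive and 4 unassessed: 8 × 12/16 = 6.0 as written, 8.0 prorated.

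**2. Effect on one subject's change.** With true LEI 3 at both visits and 2 sites unassessed only at Week 16, the expected change is 2.0 − 3 = −1.0 although nothing changed. With true LEI 4 at both visits and 2 sites unassessed only at baseline, the scored baseline averages 4 × 4/6 = 2.67, and the expected change is 4 − 2.67 = +1.33.

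**3. Effect on the treatment difference.** Let a share q of post-baseline sites be unassessed, unrelated to arm or findings, with complete baselines. Each arm's expected post-baseline score is multiplied by (1 − q). The baseline means are equal by randomization and cancel, so the expected difference becomes (1 − q) × the true difference. For scale only: one site missed in every examination gives q = 1/6 and a factor of 0.83. One site missed in one examination of ten gives q = 1/60 and a factor of 0.98.

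**4. PASDAS.** The LEI term is 1.5 × 0.23 × ln(LEI + 1). Scoring 2 instead of 3 lowers PASDAS by 1.5 × 0.23 × ln(4/3) = 0.10.

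**5. Bias against noise.** Root mean square error (RMSE) of one LEI score over all ways of leaving m sites unassessed, shown as written → prorated:

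| True LEI | m = 1 | m = 2 | m = 3 |
|---|---|---|---|
| 1 | 0.41 → 0.45 | 0.58 → 0.71 | 0.71 → 1.00 |
| 2 | 0.58 → 0.57 | 0.89 → 0.89 | 1.18 → 1.27 |
| 3 | 0.71 → 0.60 | 1.18 → 0.95 | 1.64 → 1.34 |

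Example, true LEI 1 and m = 1: as written √(1/6) = 0.41; prorated √(5/6 × 0.2² + 1/6 × 1²) = √0.20 = 0.45.

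**6. Why MDA is left alone.** Take one unassessed site and the cut-off of 1 or less. The current rule classifies every true LEI of 1 correctly and 4/6 = 67% of true LEI 2. Under proration, one affected site among five becomes 1.2 and fails the cut-off, so 5/6 = 83% of true LEI 1 would be misclassified. Proration would exchange one error for a larger one.

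**The case against.** The strongest objection is that nobody knows whether this happened. The documents give no rate of partial enthesitis examinations and name no source of them. The trial stopped after 67 subjects in four arms, LEI is analysed in a subgroup, p-values are nominal (SAP 3.4), and by-subject listings of components (SAP 6.4.2) could show recorded gaps. All of this stands, and it keeps the point small.

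Second, using the available data does not exclude proration. That is true: zero scoring follows from the word sum with no scaling stated. But two programmers could then derive different values for a key secondary endpoint, so the rule still needs completing.

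Third, proration is noisier at low scores. This also stands, as the table shows.

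A reader might infer three stronger things:
- **A false filgotinib benefit.** The spurious improvement in step 2 is within a subject. Nothing in the documents ties unassessed sites to arm, and without that link the difference between arms shrinks.
- **The same error in LDI, TDC and mNAPSI.** For LDI, "then the missing individual scores for those fingers or toes will not be included in the total LDI score"; for TDC, "then the missing count for those fingers or toes will not be included in the TDC"; for mNAPSI, "In case of one or more missing digits, the available digits will be used to calculate mNAPSI". These can mean fingers or toes that are absent, which is harmless. Protocol Appendix 24 groups missing joints with replaced ones, to be documented at Day 1 and left out afterwards. Protocol Appendix 25 measures only digits that look dactylitic, so an unmeasured digit adding 0 is ordinary LDI scoring. The wording is ambiguous, but no scoring error is shown.
- **Inflated MDA response.** A true LEI of 2 with one unassessed site would pass the criterion with probability 1/3. That alters MDA only if exactly four of the other six criteria are met, and no MDA figure can be derived from the documents.

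**Conclusion.** The point holds for LEI and SPARCC and is minor. Followed as written, the two rules score an unassessed site as unaffected and pass the partial score on as complete, while the SAP treats joint counts and FACIT-Fatigue otherwise. The bias per affected examination is definite under random missingness: 0.5, 1.0 or 1.5 points at true LEI 3 with 1, 2 or 3 sites unassessed. Its overall size is unknown because q is not given.

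Attenuation by (1 − q) rests on complete baselines and on missingness unrelated to arm and findings. If missingness depended on arm, the direction could differ, but the documents give no reason to expect that. For LDI, TDC and mNAPSI the conclusion is limited to unclear wording.

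**What to change.** 1. For the LEI and SPARCC change endpoints, and for LEI in PASDAS, use (sum / number of sites assessed) × 6 or × 16 if at least half the sites are assessed (3 of 6, 8 of 16). Otherwise set the score to missing.
2. Keep the LEI = 0 assumption in SAP 6.4.1.2, which covers the case "If a subject did not have enthesitis at baseline and hence no enthesitis assessments are collected post-baseline".
3. Leave the MDA criterion and its missing-data rule unchanged.
4. In SAP 6.3.1.7, 6.4.1.1 and 6.4.1.6, state whether missing means an absent digit or one not assessed at that visit.
5. The SAP is already signed, so document the change in the clinical study report, as SAP section 1 provides.

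The cost is a few sentences and a small derivation change. Some scores become non-integer or missing, in an already small subgroup. Precision is lost at true LEI 1, and at true LEI 2 when 3 sites are unassessed. Two versions of LEI will coexist, prorated for change and PASDAS and unscaled for MDA, and must be labelled. Proration cannot repair a baseline at which every assessed site is negative, since 0 prorates to 0.

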6.3.1.4. Psoriasis Area and Severity Index (PASI)

PASI score is used to measure the severity and extent of psoriasis. The representative site of psoriasis is selected for each body region (head and neck (h), upper limb (u), trunk (t) and lower limbs (l)), and are separately scored by using 3 parameters, erythema (redness) (E), induration (thickness) (I) and desquamation (scaling) (D), each of which is graded on a severity scale of 0 to 4 (0 = none, 1 = mild, 2 = moderate, 3 = severe and 4 = very severe). The area-wise percentage involvement of the involved sites (head and neck (Ah), upper limbs (Au), trunk (At), and lower limbs (Al)) is calculated as: 0 = no involvement, 1 = >0–< 10%; 2 = 10 – < 30%; 3 = 30 – < 50%; 4 = 50 – < 70%; 5 = 70 – < 90%; and 6 = 90 – 100%.

The final formula for PASI score is:

$$\text{PASI} = 0.1 \times (E_h + I_h + D_h) \times A_h + 0.2 \times (E_u + I_u + D_u) \times A_u + 0.3 \times (E_t + I_t + D_t) \times A_t + 0.4 \times (E_l + I_l + D_l) \times A_l$$

The PASI score ranges between 0 (no disease) and 72 (maximal disease), but is considered unreliable when BSA < 3%.

If any of the components is missing, then PASI score remains missing.

Percent improvement from baseline at a postbaseline visit is defined the same as in section 6.2.1.1. If the baseline value is 0 then the percent improvement from baseline is set to missing.

PASI75 response is defined for subjects achieved 75% improvement from Baseline in PASI score.

The summaries and analysis of PASI score will be conducted on the FAS subjects with psoriasis covering at least 3% of the BSA at Baseline.

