Appendix 20. PASI including BSA: Psoriasis Area and Severity Index including Body Surface Area

Psoriasis Area and Severity Index (PASI), Including Body Surface Area (BSA)

Intensity

A representative area of psoriasis is selected for each body region (head and neck, upper limbs, trunk, lower limbs). The intensity of erythema, induration and scaling of the psoriasis is assessed as none (0), mild (1), moderate (2), severe (3) or very severe (4).

Body surface area

The percentage area affected by psoriasis is evaluated in the 4 regions of the body. In each region, the area is expressed as nil 0 (0), >0 - <10% (1), 10 - <30% (2), 30 - <50% (3), 50 - <70% (4), 70 - <90% (5) or 90 - 100% (6)

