6.4.1.5. Physician's Global Assessment of Psoriasis (PhGAP)

The physician will give a score on the subject's psoriasis disease activity, according to the following grades:

- Induration (I) (0 – 5 scale, averaged over all lesions),
- Erythema (E) (0 – 5 scale, averaged over all lesions),
- Scaling (S) (0 – 5 scale, averaged over all lesions).

The sum of the 3 grades will be divided by 3, i.e., $= (I + E + S)/3$, and rounded to the nearest integer (i.e., 0, 1, 2, 3, 4, 5) to obtain the total average score. Physician's Static Global Assessment (0 – 5 scale) will be based on the total average score: 0 = cleared; 1 = minimal; 2 = mild; 3 = moderate; 4 = marked; and 5 = severe.

If any of the grades above is missing, then the score remains missing.

Physician's Static Global Assessment (0-5 scale) will be the endpoint for analysis, which will be considered as continuous endpoint. The summaries and analyses will be conducted on the FAS subjects with psoriasis covering at least 3% of the BSA at Baseline.

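### SAP 6.3.1.4 sets PASI to missing even when the only blank items lie in a region with area score 0, where the score is already determined

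*SAP*

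**What the plan says.** SAP 6.3.1.4 builds PASI from four regions (head and neck, upper limbs, trunk, lower limbs). Each region contributes a weight times the sum of erythema (E), induration (I) and scaling (D), times an area score A. The area score "is calculated as: 0 = no involvement", rising to 6. The missing-data rule is: "If any of the components is missing, then PASI score remains missing".

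On how severity is graded, Protocol Appendix 20 says: "A representative area of psoriasis is selected for each body region". The same appendix and SAP 6.3.1.4 both include a severity grade of 0 for none.

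PASI75 at Week 16 is a key secondary endpoint. SAP 6.3.2 gives its response rates and p-value on observed cases. Multiple imputation is planned only for the Week 12 ACR20 analyses (SAP 6.2.2 and the non-inferiority test in 6.3.2), and SAP 6.5 rules out sensitivity analyses.

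For dactylitis the SAP does write a rule for absent disease (6.3.1.7): "For subjects with dactylitis status absent for all the fingers and toes, their total LDI scores will be set as 0". No equivalent is written for PASI.

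**The concern.** When A = 0 the region's term is known to be 0, so blank severity items in that region carry no missing information about the score. The rule nevertheless turns the whole PASI into a missing value.

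A blank there is possible. Severity is rated on a representative area of psoriasis, and a clear region has none to rate.

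At Week 16, a region that was involved at baseline reaches A = 0 because it has cleared, and clearing is how subjects become responders. Any loss of this kind would therefore be related to outcome and would pull observed PASI75 and PASI100 rates down. A blank in a region that was never involved would also remove the baseline PASI. That loses information but is not itself tied to response.

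MDA and VLDA use PASI as their skin criterion for subjects with baseline involvement of 3% or more of body surface, so the loss can carry through to them.

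**Working it through.** **Inputs.** Formula, weights, score ranges and missing rule: SAP 6.3.1.4. MDA and VLDA definitions: SAP 6.3.1.5 and 6.4.1.3. Observed-case rule: SAP 6.1 and 6.3.2. Enrolment of 67 and the 2:2:1:2 ratio: SAP 1.3 and 1.2.

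**The plan's own figure.** PASI = 0.1(E+I+D)A for head and neck + 0.2(E+I+D)A for upper limbs + 0.3(E+I+D)A for trunk + 0.4(E+I+D)A for lower limbs. With every grade 4 and every area 6, this is (0.1+0.2+0.3+0.4) × 12 × 6 = 72. With all zeros it is 0. The stated range of 0 to 72 is reproduced.

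**A clear region is determined.** With A = 0 the term is weight × (E+I+D) × 0 = 0 for every severity sum from 0 to 12.

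**Worked records.** Take a baseline with areas 1, 2, 1, 2 and a severity sum of 6 in each region: 0.6 + 2.4 + 1.8 + 4.8 = 9.6. PASI75 then needs a score of at most 0.25 × 9.6 = 2.4.

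| Post-baseline record | SAP rule | Rule with area 0 contributing 0 |
|---|---|---|
| All areas 0, severity recorded as 0 | 0 (100% improvement) | 0 (100%) |
| All areas 0, severity blank | missing | 0 (100%) |
| Head area 0 with severity blank; other areas 1, severity sum 1 | missing | 0.2+0.3+0.4 = 0.9; (9.6−0.9)/9.6 = 90.6% |
| Head area 1 with one severity item blank; other areas 0 | missing | missing |

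Rows two and three are PASI75 responders that the written rule discards. Row two is also a PASI100 responder. Row one shows that nothing is lost when zeros are recorded. Row four shows that the amended rule still treats a real gap as missing.

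**MDA and VLDA with PASI missing.** The other six criteria give 2^6 = 64 met/not-met patterns.

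- 5 or 6 met: 6 + 1 = 7 patterns, MDA is yes regardless of skin.
- 3 or fewer met: 1 + 6 + 15 + 20 = 42 patterns, MDA is no regardless.
- Exactly 4 met: 15 patterns, MDA is missing.

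A cleared subject with 4 others met truly has 4 + 1 = 5 criteria and is an MDA responder. VLDA is undetermined in one pattern only, all six others met, which for a cleared subject is a true VLDA responder. So for cleared subjects these losses remove responders only, but in limited patterns.

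**Size, on assumed figures.** 67 subjects at 2:2:1:2 is about 19/19/10/19 per arm. The number with enough baseline skin disease is not given, so a range of evaluable subjects is shown, with about half truly responding and 1, 2 or 3 cleared responders lost.

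| Evaluable | True rate | 1 lost | 2 lost | 3 lost |
|---|---|---|---|---|
| 8 | 4/8 = 50.0% | 3/7 = 42.9% | 2/6 = 33.3% | 1/5 = 20.0% |
| 12 | 6/12 = 50.0% | 5/11 = 45.5% | 4/10 = 40.0% | 3/9 = 33.3% |
| 19 | 10/19 = 52.6% | 9/18 = 50.0% | 8/17 = 47.1% | 7/16 = 43.8% |

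**Extreme case.** A simulation assumed true PASI75 rates of 12.7% and 45.8%, every region involved at baseline, and every clear region left blank. It gave observed-case rates of 8.4% and 28.8%, so the difference shrinks from 33.1 to 20.4 points. Every input is assumed. This illustrates an upper bound under full blanking and is not a forecast for this trial.

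**The case against.** The strongest reply is that the premise is not in the documents. Both provide a severity grade of 0 for none. SAP 6.3.1.4 describes a score of 0 as no disease and has a rule for a baseline value of 0, so the plan expects PASI 0 to be recordable. Detailed instructions sit in electronic assessment materials that are not available here (Protocol 6.6.3.2). This stands, and it makes the harm conditional. Full blanking also looks unlikely: if regional involvement were, say, 60%, 85%, 75% and 90%, independently, then 1 − 0.60×0.85×0.75×0.90 = 66% of subjects would have no baseline PASI, which would be hard to overlook.

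The comparison with LDI is also imperfect. Protocol Appendix 25 has only dactylitic-looking digits and their contralateral digits measured, so LDI needs a zero rule by design. No such conditional collection is described for PASI. The comparison shows that the SAP knows how to write such a rule, not that leaving it out for PASI was an oversight.

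SAP 6.1 applies the same strictness to continuous composites. However, the ones it lists (DAS28(CRP), PASDAS, DAPSA) are sums, in which no component can make another irrelevant as an area of 0 does.

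A reader might infer that cleared subjects will drop out, or that PASI100 cannot be observed. Neither follows unless severity is actually left blank. A reader might also extend the point to PhGAP because SAP 6.4.1.5 says "If any of the grades above is missing, then the score remains missing". That is not supported: Protocol Appendix 22 defines grade 0 for each item as no evidence of the sign, and the SAP maps a score of 0 to cleared.

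Finally, the trial stopped at 67 subjects, p-values are nominal, and listings of endpoints with their components (SAP 6.4.2) could reveal such blanks. This lowers the stakes but does not correct the derived rates.

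**Conclusion.** The point holds as a conditional defect in a scoring rule. It is certain that the written rule has no exception for area score 0, and that the formula fixes such a region's contribution at 0. It is not established that severity is ever left blank there. If the tool always records 0, the effect is nil. If blanks occur, known PASI values are discarded, mainly in subjects whose skin improved, and neither imputation nor a sensitivity analysis recovers them.

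On the assumed counts above, one lost responder moves an arm's PASI75 rate by about 3 to 7 percentage points (52.6% to 50.0% with 19 evaluable; 50.0% to 42.9% with 8). For a cleared subject, MDA is lost only with exactly 4 of the other 6 criteria met, and VLDA only with all 6 met. Inferential weight is low because the analyses are nominal, but the descriptive rates are still reported.

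**What to change.** In SAP 6.3.1.4, replace the missing-component sentence with:

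*If a region's area score is 0, that region contributes 0 whether or not E, I and D are recorded; PASI is missing only if an area score is missing, or if E, I or D is missing in a region with area score > 0.*

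It would also help to confirm whether the assessment tool requires or fills severity 0 in clear regions. If it does, the new wording alters no result. The cost is one sentence and a small change to the derivation program, with no new data. SAP Section 1 already provides for changes after finalization to be documented in the CSR. PhGAP needs no change.
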